4.3 Supportive Care Guidelines

Supportive therapy for neutropenia:

If grade 3 or 4 neutropenia develops (ANC<1000/uL), G-CSF (Neupogen) can be administered, at the discretion of the treating investigator, until resolution of neutropenia. Neulasta (PEG-filgrastim) 6mg SC for 1 dose is recommended. If Neulasta is given, chemotherapy cannot be administered within 14 days. Neupogen can also be given at the discretion of the treating investigator. NOTE: Neupogen can be given any time before or after chemo. HOWEVER, Neulasta cannot be given within 14 days of chemotherapy.

Supportive therapy for neuropathy

Gabapentin or similar medications can be given at the discretion of the treating physician per institutional practice.

Dose Delays & Dose Modifications

Toxicities will be graded using NCI CTCAE version 4.03 (see Appendices). Dose delays and modification of lenvatinib and Eribulin are summarized below (for post-DLT period in phase II patients only). Individual patient dose reductions are also provided in separate tables.

Dose Delay & Modification for Eribulin and Lenvatinib

Toxicity	Adverse event	Dose Reduction/Delay	
		Eribulin	Lenvatinib
Hematologic toxicity attributed to any or all treatment	Platelets 75000-99999/mm ³ within 24 hrs prior to scheduled therapy	If Day 1: Hold until recovery of platelets >100,000/mm ³ . Resume at the same level after recovery If Day 8: No intervention	No dose modification necessary
	ANC <1000/mm ³ or Platelets 25000-74999/mm ³ within 24 hrs prior to scheduled therapy	If Day 1: Hold until recovery to ANC >1000/mm ³ and Platelets 100000/mm ³ . Resume at same level after recovery If Day 8: Hold until recovery to ANC >1000/mm ³ and Platelets 75000/mm ³ . Resume at same level after recovery	Hold until recovery to ANC >500/mm ³ and platelets more than 25000, Resume at same level after recovery.
	Platelets <25000/mm ³ or Platelets 25000-50000/mm ³ complicated by bleeding, easy bruising, petechiae, or requiring platelet transfusion	If Day 1: Hold until recovery to Platelets 100000/mm ³ . Resume at same level after recovery If Day 8: Hold until recovery to Platelets 75000/mm ³ . Resume at same level after recovery	Hold until recovery of Platelets 25000/mm ³ . Resume at current dose level.

	Prolonged neutropenia (ANC<500/mm ³ for >7 days)	Hold until recovery to ANC>1000/mm ³ . Resume at one dose level below current dose level	Hold until recovery to ANC>500/mm ³ . Resume at same level dose.

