	Febrile neutropenia (ANC <1000/mm ³ with temperature of >38.5°C)	Hold until recovery to ANC>1000/mm ³ . Resume at one dose level below current dose level	Hold until recovery to ANC>1000/mm ³ . Resume at same dose level
	Anemia	No reduction or delay	No reduction of delay
Hepatic toxicity	Grade 4 AST, ALT or Total Bilirubin Child Pugh Score	For patients with known liver dysfunction and Child Pugh score A, Eribulin should be started at a dose of 1.1mg/m ² . For patients with known liver dysfunction and Child Pugh score B, Eribulin should be started at a dose of 0.7mg/m ² . Eribulin should not be administered in patients with Child Pugh score C. If during treatment there is grade 3,4 liver toxicity then dose reduce by 1 dose level.	Hold until recovery to Grade 1 or baseline. Resume at reduced dose of 20 mg po daily if first occurrence, reduce to 14 mg po daily on second occurrence and 10 mg po daily on third occurrence.

Peripheral neuropathy	Grade 3 or 4	Hold until recover to \leq grade 2. Reduce dose by one dose level. If neuropathy fails to recover to grade 2 within 3 weeks, Eribulin should be discontinued.	No modifications necessary
Non-hematologic toxicity grade 3 or 4 attributed to any or all treatment (except for neuropathy)	Grade 3 or 4 nausea/vomiting despite optimal antiemetic treatment	Hold until nausea/vomiting have resolved to \leq grade 1. Resume at same dose level	Hold until nausea/vomiting have resolved to \leq grade 1. Resume at same dose.
	>Grade 2 stomatitis	Hold until stomatitis has resolved to \leq grade 1. Resume at one dose level below current dose level	Hold until recovery to \leq grade 1. Resume at the same dose level
Hypertension	Grade 3 Hypertension Or life threatening Hypertension	No dose modification necessary.	Withhold lenvatinib for Grade 3 hypertension that persists despite optimal antihypertensive therapy; resume at one dose level below current dose level. Discontinue for life threatening hypertension.
Cardiac dysfunction or Hemorrhage.	Grade 3 or Grade 4 events	No dose modification necessary	Withhold lenvatinib for development of Grade 3 event until improved to Grade 0 or 1 or baseline. Either resume at a reduced dose or discontinue lenvatinib depending on the severity and persistence of the adverse event.

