Proteinuria	>2 gms or less than 2 gms	No dose modification necessary.	Withhold lenvatinib for \leq 2 grams of proteinuria/24 hours. Resume at next dose level below current dose level; 2) when proteinuria is >2 gm/24 hours. Discontinue lenvatinib for nephrotic syndrome.
QTc Prolongation	Grade 3 or greater	No dose modification necessary	Monitor and correct electrolyte abnormalities in all patients. Withhold lenvatinib for the development of Grade 3 or greater QT interval prolongation. Resume lenvatinib at a one dose level below previous dose level when QT prolongation resolves to Grade 0 or 1 or baseline.

Day 8 dose of Eribulin may be delayed for a maximum of 1 week. If toxicities do not improve enough after 1 week delay then omit day 8 dose of Eribulin. If day 8 of Eribulin is omitted two consecutive cycles Eribulin should be resumed at one dose below current dose level.

Eribulin Dose Modifications

Starting dose and dose modifications for unacceptable toxicity that is thought to be related to Eribulin are listed below. Dose adjustments are to be made according to the greatest degree of toxicity. The most common toxic effects of Eribulin are fatigue, neutropenia (including neutropenic fever), peripheral neuropathy, and alopecia.

Eribulin Dose Modifications, TABLE 1

0	1.4
-1	1.1
-2	0.7

NOTE: Patients requiring a third dose reduction should be taken off study unless in the opinion of the investigator and/or the DSMB there is reason to believe that the patient is still experiencing clinical benefit (in such cases the DSMB will issue written approval).

Lenvatinib Dose Modifications

Recommended Dose Modifications for Persistent and Intolerable Grade 2 or Grade 3 Adverse Reactions or Grade 4 Laboratory Abnormalities, TABLE 2

0	20
-1	14
Note: Based on toxicity data of 1st 10 patients in Phase 2, starting Lenvatinib dose was not increased to 24 mg daily	

Other Toxicities with Lenvatinib

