¹¹Lenvatinib may cause proteinuria. Patients with 2+ or greater urine dipstick reading should undergo further assessment with a 24-hour urine collection. If 24hr urine protein ≥ 2 g then suspend lenvatinib until it decreases to <2 g and dose reduce by one dose level. If nephrotic syndrome then permanently discontinue lenvatinib.

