5.5 Proteinuria

In Study 1, proteinuria was reported in 34% of LENVIMA-treated patients and 3% of patients in the placebo group [*see Adverse Reactions (6.1)*]. The incidence of Grade 3 proteinuria in LENVIMA-treated patients was 11% compared to none in the placebo group.

Monitor for proteinuria before initiation of, and periodically throughout treatment. If urine dipstick proteinuria greater than or equal to 2+ is detected, obtain a 24 hour urine protein. Withhold LENVIMA for ≥ 2 grams of proteinuria/24 hours and resume at a reduced dose when proteinuria is < 2 gm/24 hours. Discontinue LENVIMA for nephrotic syndrome [*see Dosage and Administration (2.2)*].

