2.2 Dose Modifications

Hypertension

- Assess blood pressure prior to and periodically during treatment. Initiate or adjust medical management to control blood pressure prior to and during treatment.
- Withhold LENVIMA for Grade 3 hypertension that persists despite optimal antihypertensive therapy; resume at a reduced dose (*see Table 1*) when hypertension is controlled at less than or equal to Grade 2.
- Discontinue LENVIMA for life-threatening hypertension.

Cardiac dysfunction or hemorrhage

- Discontinue for a Grade 4 event.
- Withhold LENVIMA for development of Grade 3 event until improved to Grade 0 or 1 or baseline.
- Either resume at a reduced dose (*see Table 1*) or discontinue LENVIMA depending on the severity and persistence of the adverse event.

Arterial thrombotic event

- Discontinue LENVIMA following an arterial thrombotic event.

Renal failure and impairment or hepatotoxicity

- Withhold LENVIMA for development of Grade 3 or 4 renal failure/impairment or hepatotoxicity until resolved to Grade 0 to 1 or baseline.

- Either resume at a reduced dose (*see Table 1*) or discontinue LENVIMA depending on the severity and persistence of renal impairment or hepatotoxicity.
- Discontinue LENVIMA for hepatic failure.

Proteinuria

- Withhold LENVIMA for ≥ 2 grams of proteinuria/24 hours.
- Resume at a reduced dose (*see Table 1*) when proteinuria is < 2 gm/24 hours.
- Discontinue LENVIMA for nephrotic syndrome.

Gastrointestinal perforation or fistula formation

- Discontinue LENVIMA in patients who develop gastrointestinal perforation or life-threatening fistula.

QT prolongation

- Withhold LENVIMA for the development of Grade 3 or greater QT interval prolongation.
- Resume LENVIMA at a reduced dose (*see Table 1*) when QT prolongation resolves to Grade 0 or 1 or baseline.

Reversible posterior leukoencephalopathy syndrome (RPLS)

- Withhold for RPLS until fully resolved.
- Upon resolution, resume at a reduced dose or discontinue LENVIMA depending on the severity and persistence of neurologic symptoms.

Manage other adverse reactions according to the instructions in Table 1. Based on the absence of clinical experience, there are no recommendations on resumption of dosing in patients with Grade 4 clinical adverse reactions that resolve.

Table 1 Recommended Dose Modifications for Persistent and Intolerable Grade 2 or Grade 3 Adverse Reactions or Grade 4 Laboratory Abnormalities^a

Adverse Reaction	Modification	Adjusted Dose ^b

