DLT evaluation will occur weekly for the first cycle (1 cycle = 21 days).

Any enrolled and treated patient should be evaluated for DLT purposes.

The DLT period as a whole will be the first cycle of treatment. (Adverse events, however, will continue to be collected for the duration of treatment).

In general, a non-hematologic DLT is defined as any Grade ≥ 3 toxicity, and a hematologic DLT is defined as any Grade ≥ 4 toxicity, both by CTCAE v4.03 criteria.

In addition, the following criteria and exceptions apply:

- ANC $< 500/\text{mm}^3$ for > 7 days despite GCSF support is a DLT.
- Platelet count $< 20,000/\text{mm}^3$ for more than 3 days that is considered drug-related is a DLT.
- For nausea, vomiting, or diarrhea, patients must have Grade 3 or 4 toxicity that persists at this level despite use of optimal symptomatic treatment (per local institutional guidelines), in order for these to be considered a DLT.
- Grade 3 thromboembolic events are not considered DLT.
- Any Grade 3 rash that resolves to Grade ≤ 2 within a 10 day period (including with symptomatic treatment) will not be considered a DLT.
- Cases involving hyperbilirubinemia that is primarily indirect, and considered not reflective of underlying liver disease (ie, resulting from transfusion of red blood cells), will not be considered a DLT.
- A DLT must be attributed to one of the two investigational drugs. A “drug-related toxicity” includes as events, any toxicity considered related, probably related, or possibly related to study drugs. Toxicities clearly not related to the drug, such as disease progression, environmental, unrelated trauma may not be considered “drug related toxicity”

- As per the Mays Cancer Center DSMP, any protocol modifications, problematic safety reports, unanticipated problems, and suspension or early termination of a trial must be reported to the DSMB #2 and all members of the research team at UT Health San Antonio and all affiliate sites. Furthermore, the PI of this study will promptly notify all study affiliates, the UT Health San Antonio IRB, the Mays Cancer Center DSMC, and the FDA via a FDA Form 3500Aa written IND safety report of any adverse events that are either serious and/or unexpected. Suspension and early termination of a trial must also be reported immediately to the Director of Quality Assurance who will promptly notify the sponsor and the UT Health San Antonio IRB.

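### Section 4.3 reverses the lenvatinib hold for proteinuria and prints the 20 mg starting dose as the first hepatic dose reduction

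*Combined protocol and SAP*

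**What the plan says.** Section 4.3 states that its delay-and-modification table is "for post-DLT period in phase II patients only", and adds: "Individual patient dose reductions are also provided in separate tables". Appendix III fixes the DLT window: "The DLT period as a whole will be the first cycle of treatment". The table therefore governs phase II dosing after cycle 1.

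**Proteinuria.** The event cell names values above and below 2 g and so sets no threshold. The lenvatinib cell withholds at ≤2 g/24 h, continues "Resume at next dose level below current dose level; 2) when proteinuria is >2 gm/24 hours", and stops the drug for nephrotic syndrome. Footnote 11 to the section 6.0 schedule orders a 24-hour collection after a dipstick of 2+ or more. If the result is 2 g or more, it says "then suspend lenvatinib until it decreases to <2 g and dose reduce by one dose level". The appended label takes the same line as footnote 11. Appendix I, section 5.5, withholds at 2 g or more "of proteinuria/24 hours and resume at a reduced dose when proteinuria is" below 2 g. Appendix I, section 2.2, repeats it: "Resume at a reduced dose (*see Table 1*) when proteinuria is" below 2 g.

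**Hepatic toxicity.** The trigger is "Grade 4 AST, ALT or Total Bilirubin". Lenvatinib is held until grade 1 or baseline, then resumed at 20 mg after the first occurrence, 14 mg after the second and 10 mg after the third. Table 2 in the same section includes grade 4 laboratory abnormalities in its heading. It lists level 0 as 20 mg and level −1 as 14 mg, with nothing lower, and its note records that the starting dose was not raised to 24 mg. Section 7.2 also gives 20 mg daily.

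**The concern.** These are instructions that sites act on. Section 12.0 requires the study to be run as the approved protocol describes, but a site cannot obey both the proteinuria cell and footnote 11, or both the hepatic cell and the step-down that Table 2 implies. The trial is multi-center, so sites may resolve the conflicts differently.

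Taken literally, the proteinuria cell withholds drug from patients with little or no proteinuria and allows a restart above the level at which the label stops it. The hepatic cell returns a patient to the full lenvatinib starting dose after grade 4 liver laboratory toxicity while describing this as a reduction.

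Proteinuria is not rare on lenvatinib. Appendix I, section 5.5, reports 34% at any grade and 11% at grade 3. Those figures come from 24 mg monotherapy in thyroid cancer, so they are context and not an estimate for this regimen.

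**Working it through.** No plan figure has to be reproduced to test this point. The check sets the printed rules side by side.

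**Proteinuria.** Let x be the 24-hour protein in grams. Inputs: the lenvatinib cell of the section 4.3 proteinuria row, and footnote 11 of section 6.0.

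| x | Section 4.3 cell | Footnote 11 |
|---|---|---|
| x < 2 | withhold | no hold; a held patient may restart one level lower |
| x = 2 | withhold | withhold |
| x > 2 | restart condition met | withhold |

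The hold regions are x ≤ 2 and x ≥ 2, and they overlap only at x = 2. The hold sign and the restart sign are both reversed, so one misread character would not explain the cell.

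**Hepatic toxicity.** Inputs: starting dose 20 mg (section 7.2 and the Table 2 note); the row's doses of 20, 14 and 10 mg; Table 2 levels of 20 and 14 mg; and Appendix I, section 2.2, Table 1, whose footnote b takes each reduction from the previous dose.

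- Label ladder from 24 mg: 24 − 20 = 4 mg (4/24 = 17%); 20 − 14 = 6 mg (6/20 = 30%); 14 − 10 = 4 mg (4/14 = 29%).
- The row from this trial's 20 mg start: 20 − 20 = 0 mg; 20 − 14 = 6 mg; 14 − 10 = 4 mg.
- Table 2, one level down at the first occurrence: 20 − 14 = 6 mg (30%).

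The row reproduces the label's 20/14/10 sequence, whose first step starts from 24 mg. That step does not exist here, so the row runs one step behind. Applying the label's own footnote from 20 mg also gives 14 mg.

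At the second occurrence the row gives 14 mg. The comparator depends on a decision the protocol has not made. If 10 mg is added as level −2, the row is 14 − 10 = 4 mg higher (4/10 = 40%). If it is not added, the comparator is discontinuation.

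**Other rows.** The hypertension and QTc rows each step lenvatinib down by one level, which is the pattern the hepatic row lacks.

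**Statistical design.** The section 8.1.2 rule (n = 30, reject at 10 or more responses, 0.20 against 0.40) recomputes to alpha 0.0611 and power 0.8237, as printed. Neither cell enters that calculation.

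**The case against.** The strongest reply is that the correct proteinuria rule is already in the protocol, and in the right place. A site obtains a 24-hour value because footnote 11 tells it to, and the next sentence gives the correct action. A rule that withholds drug from patients without proteinuria is plainly unworkable, and many clinicians would notice. The cell, the footnote and the label all agree on stopping for nephrotic syndrome. Above 2 g the cell supplies only a restart condition; it does not order continued dosing in a patient who has not been held. All of this stands and limits the likely harm. It still leaves two incompatible operative rules in force.

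On the hepatic row, Table 2 has no occurrence column, so 14 mg at the first occurrence is a reading of its levels. The rows for nausea/vomiting, stomatitis and hematologic toxicity resume lenvatinib at the same dose. The hepatic row also holds lenvatinib until recovery and lowers eribulin by one level for grade 3 or 4 liver toxicity, so the regimen as a whole is reduced. These points are fair, but the row itself calls 20 mg a reduction from a 20 mg start, and same-dose rules for other toxicities do not change that.

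Section 4.7 takes a patient off therapy for grade 4 toxicity after two dose modifications, which bears on the later steps. It is unclear whether 20 mg to 20 mg counts as a modification. Either choice for the 10 mg step is compatible with that rule. Separately, the label holds for hepatotoxicity from grade 3, whereas this row starts at grade 4; correcting the dose leaves that question open.

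**Conclusion.** The concern holds for both cells, and they should be corrected before further use. The proteinuria hold conflicts with footnote 11 at every 24-hour value except exactly 2 g. The first hepatic reduction is 0 mg, against 6 mg (30%) for one level down in Table 2. The hepatic comparison assumes a 20 mg start, which section 7.2 and the Table 2 note support, and a one-level step, which the label footnote and the hypertension and QTc rows support. The second-occurrence difference remains conditional on what the sponsor decides about 10 mg.

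No number of affected patients can be given. The documents contain no proteinuria rate for this regimen after cycle 1 and no rate of grade 4 AST, ALT or bilirubin, and how often sites would follow the cells literally is unknown. This is a patient-safety drafting error with no effect on sample size, alpha, power or analysis.

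**What to change.** - **Proteinuria row.** Set the event to 24-hour protein of 2 g or more. Lenvatinib cell: withhold at 2 g/24 h or more; restart one level lower once the value is under 2 g/24 h; stop permanently for nephrotic syndrome.
- **Hepatic row, lenvatinib cell.** Keep the hold to grade 1 or baseline, and replace the 20/14/10 mg sequence with a restart one level lower, which is 20 mg to 14 mg at the first occurrence.
- **Table 2.** Choose one: add 10 mg as level −2, or drop the 10 mg step and state beneath the table that lenvatinib is discontinued if a patient on 14 mg needs a further reduction. Placed there, the statement also covers the hypertension, QTc and proteinuria rows.

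The cost is an amendment to two table rows and one line or note at Table 2, IRB approval before implementation (section 12.0), and a notice to sites. The statistical section needs no change.

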4.4 Concomitant medications

All concomitant treatments, including blood and blood products, must be reported in the patient's electronic medical record.

4.5 Not Permitted

Patients who are taking any herbal (alternative) medicines are NOT eligible for participation. Patients must be off any such medications by the time of registration. Patients who are undergoing concomitant radiotherapy or chemotherapy are NOT eligible for participation. Patients may not have received Eribulin or lenvatinib previously. Length of the washout period from prior chemotherapy or radiation therapy will be 14 days.

4.6 Permitted

Supportive care, including but not limited to anti-emetic medications, may be administered at the discretion of the treating physician. Concurrent treatment with bisphosphonates or denosumab is allowed. Erythropoietin may be administered at the discretion of the investigator, consistent with institutional guidelines. G-CSF should be administered according to the guidelines in this protocol.

4.7 Duration of Therapy

Patients may continue on study therapy until disease progression or until unacceptable toxicity occurs.

Patients will go off study therapy if any of the following occurs:

- The patient experiences any grade 4 toxicity after 2 dose modifications, as recommended by the protocol. If treatment is held for 2 consecutive treatment cycles due to toxicity, the patient must go off treatment.
- The patient withdraws consent from treatment or from the study as a whole.
- There is disease progression.
- The treating physician feels it is necessary (e.g. due to patient non-compliance or other safety concerns).

4.8 Follow-up Post Therapy

Patients will be followed every 6 months at the time of routine clinic visit or via phone call with study personnel after completion of treatment until death.

Treatment after study completion will be left to the discretion of the treating physician(s) and will not be considered part of this study. However, patients should still be followed for study endpoints including date of progression and survival status.

5.0 Response Assessment

Patients with measurable disease are eligible for the study. Response to treatment will be assessed using RECIST 1.1 guidelines. Response and progression will be assessed in this study via physical exam and imaging.

5.1 Definitions

5.1.1 Measurable disease

Measurable lesions are defined as those that can be accurately measured in at least one dimension (longest diameter to be recorded) as >20 mm with conventional techniques or as >10 mm with spiral CT scan.

5.1.2 Non measurable disease

All other lesions or sites of disease, including small lesions (those with a longest diameter of < 20 mm with conventional techniques or < 10 mm with spiral CT scan) as well as those that can be assessed as to changes in size but cannot be clearly measured, are considered non-measurable disease. Other examples include bone lesions, leptomeningeal disease, ascites, pleural/pericardial effusions, lymphangitis cutis/pulmonis, inflammatory breast disease, abdominal masses (not followed by CT or MRI).

